4.5 Interim analyses and data monitoring

4.5.1 Data monitoring committee

The conduct of the study and monitoring of the safety data will be supervised by an independent DMC to optimize subjects' safety and to identify any safety signals. Full details of the composition and roles of the DMC will be provided in a separate DMC Charter.

The data to be reviewed by the DMC will be as detailed in the DMC Charter and will include unblinded safety data. The details regarding the outputs to be produced and the analyses to be performed will be provided in a separate DMC SAP.

4.5.2 Interim analysis

This study will include two informal unblinded interim analyses, the first after approximately 45 subjects have completed 4 weeks of the study and the second when the last randomized subject for this study has completed the Week 12 Visit at the end of the Treatment Period or this subject's participation has ended prematurely. This second planned interim analysis excludes the 2 subjects from site 101 who entered the study outside of the recruitment period. The purpose of these interim analyses is for sponsor key personnel to review results from the primary efficacy analysis and a subset of the analyses of exploratory efficacy and safety outcomes to facilitate additional Clinical Planning or Portfolio Management decisions. Neither interim analysis will lead to any formal decision to alter or terminate the trial.

Details on the summaries and analyses to be presented at these informal interim analyses are included in the Interim Analysis SAP.

All analyses and unblinding instructions will be pre-specified in the Interim Analysis SAP.

4.6 Multicenter studies

The data summaries and statistical analyses will not be performed by center.

4.7 Multiple comparisons/multiplicity

Not applicable.

4.8 Use of an efficacy subset of subjects

In order to investigate the impact on the efficacy analyses, the PPS will be used to evaluate the subset of subjects in the FAS with no IPDs.

4.9 Active-control studies intended to show equivalence

Not applicable.

4.10 Examination of subgroups

Not applicable.

5 STUDY POPULATION CHARACTERISTICS

5.1 Subject disposition

The number and percentage of subjects who were randomized into the study, subjects who completed or prematurely discontinued the study, as well as the primary reason for discontinuation will be presented by treatment group and for all subjects, based on the RS. A subject who completed the study is defined as a subject who completed all visits up to the last scheduled study visit, ie, Visit 12 (Week 30).

In addition, the number and percentage of subjects completing Week 4 and Week 12 of the Treatment Period will be presented. A subject is defined as completing Week 4 and Week 12, respectively, if adequate efficacy data are available in the database to calculate the primary efficacy variable at the respective visit.

The number and percentage of subjects who discontinued due to AEs will be summarized separately by treatment group and for all subjects, based on the RS. This will be used for European Union Drug Regulating Authorities Clinical Trials (EudraCT) reporting.

The number and percentage of subjects included in each of the analysis sets will be summarized by treatment group and for all subjects based on the ES. Percentages will be calculated based on the RS for the purpose of this summary.

Screen failure reasons will be summarized for the ES. A listing of subjects who did not meet study eligibility criteria (including a glossary) will also be presented for the ES.

In addition, the following listings will be presented by treatment group:

- Subject disposition (ES)
- Study discontinuation (RS)
- Visit dates (SS)
- Subject analysis sets (ES)

The listing of subject disposition will include the date of informed consent, date of pharmacogenetic informed consent (for subjects participating in the pharmacogenetic substudy), date of randomization, date and time of first and last dose of IMP, date of premature study termination and primary reason (if applicable), and date of final contact. If applicable, the date and reason for premature unblinding will also be included.

The listing of study discontinuation will include the primary reason for discontinuation and the number of days on IMP.

The number of days on IMP will be calculated as follows:

$$\text{Number of days on IMP} = (\text{Date of Last Dose Received} - \text{Date of First Dose Received}) + 1$$

5.2 Protocol deviations

Important protocol deviations will be identified and classified by the deviation types listed in the IPD document. A listing of all IPDs will be presented for all subjects in the RS and will include the deviation type and description. The number and percentage of subjects with IPDs will be summarized by treatment group and for all subjects for each deviation type (Section 5.2), based on the RS.

6 DEMOGRAPHICS AND OTHER BASELINE CHARACTERISTICS

6.1 Derivation of variables

6.1.1 Calculation of body mass index

The body mass index (BMI) in kg/m² is calculated based on the height (in m) and the weight (in kg) using the following formula:

$$BMI = \frac{Weight}{Height^2}$$

The BMI will be automatically derived by and recorded on the electronic case report form (eCRF).

6.1.2 Classification of age categories

Age will be classified into categories based on requirements for EudraCT and clinicaltrials.gov reporting.

For the EudraCT reporting, the categories will include:

- 18 to <65 years
- 65 to <85 years
- ≥85 years

For the clinicaltrials.gov reporting, the categories will include:

- ≤18 years
- 19 to <65 years
- ≥65 years

6.1.3 Duration of disease

The duration of disease will be calculated as follows and will be presented in years to 1 decimal place:

$$\text{Duration} = \text{Date of Screening} - \text{Date of HS Diagnosis}$$

In the event that the date of diagnosis is incomplete, it will be imputed to the most recent feasible date:

- If only the day is missing, it will be imputed to the last day of the known month
- If the day and month are missing, it will be imputed to December 31 in the known year
- If the date of diagnosis is completely missing, the duration of disease will not be calculated

6.2 Demographics and Baseline characteristics

A by-subject listing of Baseline demographic characteristics will be presented by treatment group. This will include the year of birth (if available), age (in years), sex, race, ethnicity, height (in cm), weight at Screening (in kg) and BMI for the ES. The age will be entered directly into the study database and will not be re-calculated for the statistical analysis.

All Baseline demographic characteristics (with the exception of year of birth) will be summarized by treatment group and for all subjects based on the SS. The summary of age will include descriptive statistics and categorical summaries, the latter based on requirements for EudraCT and clinicaltrials.gov reporting. Childbearing potential (as applicable) and lifestyle (alcohol, tobacco and caffeinated beverage use) will be listed for the SS.

6.3 Other Baseline characteristics

The following Baseline disease characteristics will be listed for the SS, based on the Baseline definitions in [Table 3–1](#) unless otherwise specified:

- Lesion counts by anatomical region and lesion type, total lesion counts across anatomical regions by lesion type, Hurley Stage by anatomical region and worst overall Hurley Stage

across anatomical regions; degree of erythema by anatomical region and worst overall erythema across all anatomical regions ([Section 8.1](#))

- IHS4 score, total HADS-A and HADS-D scores, Modified Sartorius Score, PGA of skin pain (average and worst pain over the last 24 hours), HS-Physician's Global Assessment, total DLQI score and EQ-5D-3L (domain scores, index score and VAS score) ([Section 8.3](#))
- Duration of disease at Screening, based on date of diagnosis as captured in the eCRF
- High sensitivity C-reactive protein (hsCRP)

The above Baseline disease characteristics will be summarized by treatment group and for all subjects in the FAS.

Baseline lesion counts will be summarized by lesion type and anatomical region, and total lesion counts across all anatomical regions will be summarized by lesion type.

Baseline Hurley stage and degree of erythema will be summarized by treatment group and for all subjects by anatomical region. The worst overall Hurley stage and erythema calculated across all anatomical regions will be summarized by treatment group and for all subjects.

In addition, the following Baseline disease characteristics will be summarized by Baseline Hurley Stage and overall, and treatment group, for the FAS

- IHS4 score
- Total HADS-A and HADS-D scores
- Modified Sartorius Score
- PGA of skin pain (average and worst pain over the last 24 hours)
- HS-Physician's Global Assessment
- Total DLQI score
- EQ-5D-3L (domain scores, index score and VAS score)
- Duration of disease
- hsCRP
- Total lesion counts
- Worst overall erythema

6.4 Medical history and concomitant diseases

Medical history will be listed for the RS and summarized for the SS by treatment group and for all subjects, and by MedDRA system organ class (SOC) and preferred term (PT). The reported term will be included in the listing. The summary will include the number and percentage of subjects, and will be sorted alphabetically by SOC and by descending incidence of PT within each SOC, based on the 'All Subjects' column. A glossary of all medical history conditions will be presented for the RS including the SOC, PT and reported term.

Procedure history will be listed separately by treatment group for the procedure reported term based on the RS. Concomitant medical procedures performed during the study will be listed for the RS.

6.5 Hidradenitis suppurativa history

Date of initial diagnosis of HS and the date that HS symptoms first started will be listed.

6.6 Prior and concomitant medications

Prior and concomitant medications (as defined below) will be listed for the RS by treatment group and subject, and summarized for the SS by WHODD Anatomical Main Group (Level 1), Pharmacological Subgroup (Level 3) and PT. The reported term will be included in the listing, together with flags to identify antibiotic and rescue medications, respectively. Separate summaries will be presented for prior medications and concomitant medications and these will be presented by treatment group and for all subjects. Prior medications which continued into the study period are also classified as concomitant and are included in both summaries.

Separate summaries will be presented for the following, identified using WHODD Anatomical Main Group codes, the indication recorded on the eCRF and medical review of the recorded data:

- Prior and concomitant HS medications
- Concomitant antibiotic medications at study entry
- Rescue medication during study

All HS medications, antibiotics and rescue medication given during the study will be identified via medical review of the concomitant medications and confirmed at the DEMs prior to unblinding.

Concomitant antibiotic medication at study entry is defined as any antibiotic with start date on or prior to first dosing, and end date on or after screening.

All tabulations will be sorted alphabetically by Level 1 term, alphabetical Level 3 term within Level 1 and decreasing frequency of PT in the 'All Subjects' column.

The listing will include a flag for prohibited prior and concomitant medications. These will be confirmed and documented at the final DEM.

A glossary of all prior and concomitant medications will be presented for the RS including the Anatomical Main Group (Level 1), Pharmacological Subgroup (Level 3), PT and reported term.

Any medications with partially missing dates will be handled as described in [Section 4.2.4](#) in order to classify them as prior or concomitant.

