5.1.1 Study periods

This study will include 3 periods: a Screening Period (≥ 2 weeks up to a maximum of 4 weeks prior to randomization), a Treatment Period (12 weeks), and a SFU Period (20 weeks after the last dose of IMP).

Screening Period

The Screening Period will last ≥ 2 weeks up to a maximum of 4 weeks prior to randomization (dosing cannot occur earlier than 2 weeks after Screening due to IMP shipping timelines). During this time, laboratory data (hematology, urine, and biochemistry tests) will be obtained, and other information will be collected to confirm subject eligibility for this study.

Treatment Period

During the Treatment Period, eligible subjects will be randomized 2:1:1 (bimekizumab to placebo to adalimumab, stratified by Baseline Hurley Stage) to receive blinded IMP (all administered by sc injection by unblinded study personnel).

- Subjects randomized to receive bimekizumab will receive the following:
 - 640mg at Baseline (loading dose)
 - 320mg at Weeks 2, 4, 6, 8, and 10
- Subjects randomized to receive adalimumab will receive the following:
 - 160mg at Baseline (loading dose)

- 80mg at Week 2
- 40mg at Weeks 4, 5, 6, 7, 8, 9, and 10
- Subjects randomized to receive placebo will receive placebo at Baseline (loading dose) and at Weeks 2, 4, 5, 6, 7, 8, 9, and 10

Because of differences in the dosing schedule between bimekizumab and adalimumab, placebo injections will be administered along with active drug such that all subjects will receive the same number of injections at each corresponding visit. The number of placebo and active injections will vary by visit and treatment group, as described in [Section 7.2](#) and [Table 7–1](#).

A sufficient number of subjects will be screened in order to have 80 subjects randomized in the study. There will be approximately 40 subjects in the bimekizumab treatment group, 20 subjects in the placebo group, and 20 subjects in the adalimumab group. The primary efficacy variable will be assessed at Week 12 (Visit 11).

Subjects who withdraw early from the study for any reason, including those withdrawn from IMP, will be asked to return for study assessments 12 weeks after the first dose (ie, the Week 12 Visit) and for an Early Withdrawal Visit that will comprise the same assessments as planned for the SFU Visit (Visit 12; 20 weeks after the last dose of IMP).

A Data Monitoring Committee (DMC) will review the data on an ongoing basis, as detailed in [Section 11.5](#).

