6.2 Exclusion criteria

Subjects are not permitted to enroll in the study if any of the following criteria is met:

1. Prior treatment with anti-IL17s or participation in an anti-IL17 study.
2. Subjects who previously received anti-TNFs.
3. Subjects participating in another study of a medication or a medical device under investigation within the last 3 months or at least 5 half-lives of the investigational product,

whichever is greater, or is currently participating in another study of a medication or medical device under investigation.

4. Subject has a known hypersensitivity to any excipient(s) of bimekizumab or adalimumab.
5. Subject is using concomitant oral analgesics for HS-related or non-HS-related pain at study entry:
 - Opioid analgesics within 14 days prior to the Baseline Visit.
 - Non-opioid oral analgesics *unless* at a stable dose for at least 14 days prior to the Baseline Visit (PRN use is not considered a stable dose).
6. Subject requires, or is expected to require, opioid analgesics for any reason (excluding tramadol).
7. Subject received prescription topical therapies for the treatment of HS within 14 days prior to the Baseline Visit.
8. Subject received systemic non-biologic therapies for HS with potential therapeutic impact for HS less than 28 days prior to Baseline Visit.
9. Subject has a draining fistula count >20 at the Baseline Visit.
10. Subjects with a diagnosis of inflammatory conditions other than HS, including but not limited to PSO, PsA, RA, sarcoidosis, or systemic lupus erythematosus. Subjects with a diagnosis of CD or ulcerative colitis are allowed as long as they have no active symptomatic disease at Screening or Baseline.
11. Subjects with a history of chronic or recurrent infections, or a serious or life-threatening infection within the 6 months prior to the Baseline Visit (including herpes zoster). Subjects with a high risk of infection in the investigator's opinion (eg, subjects with leg ulcers, indwelling urinary catheter, persistent or recurrent chest infections, prior prosthetic joint infection at any time, subjects who are permanently bedridden or wheelchair assisted).
12. Subject has any current sign or symptom that may indicate an active infection (except for common cold), or has had an infection requiring systemic antibiotics within 2 weeks of the Baseline Visit.
13. Any other active skin disease or condition (eg, bacterial, fungal or viral infection) that may interfere with assessment of HS.

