7.8 Concomitant medications/treatments

7.8.1 Permitted concomitant treatments (medications and therapies)

The following concomitant medications/treatments are permitted during the study:

- Antiseptic Therapy
 - Subjects are required to use a daily antiseptic wash on their HS lesions. Allowable antiseptic washes are limited to one of the following: chlorhexidine gluconate, triclosan, benzoyl peroxide, or dilute bleach in bathwater.
- Wound Care
 - Concomitant use of wound care dressings on HS wounds is allowed; however, options are limited to alginates, hydrocolloids, and hydrogels.
- Analgesic Therapy
 - Most subjects will be required to washout all analgesics for 14 days prior to Baseline. This includes analgesics for HS-related pain and other pain (non-HS-related). However, if a subject is on a stable dose of a non-opioid analgesic (PRN is not considered stable) for HS-related pain or for a non-HS medical condition (eg, osteoarthritis), the subject may continue the analgesic, provided the dose is stable for 14 days prior to Baseline and is anticipated to remain stable throughout study participation.
 - If a subject's pain (HS-related or non-HS-related) worsens after Baseline, they may initiate analgesic therapy at any time as follows: For HS-related pain, permitted analgesics are limited to: ibuprofen (at a dose of up to 800 mg po every 6 hours) not to exceed 3.2 grams/per 24 hours; AND/OR acetaminophen/paracetamol as per local labeling. If HS-related pain is uncontrolled with ibuprofen or acetaminophen/paracetamol at the above dosing regimens after the Baseline Visit (Visit 2), subjects can be prescribed tramadol (at a dose of up to 100mg po every 4 hours), not to exceed 400mg per 24 hours.
- Antibiotic Therapy
 - Concomitant use of oral antibiotic therapy for treatment of HS is allowed provided the dosing regimen (dose and frequency) has been stable for at least 4 consecutive weeks (28 days) prior to Baseline. The dosing regimen must remain stable throughout study participation. Antibiotics taken on an "as needed" (PRN) basis are not considered a stable dose.
 - Permitted oral concomitant antibiotics include:
 - Oral: doxycycline (at a dose of up to 100 mg po bid); minocycline (at a dose of up to 100 mg po bid)

- If another Baseline oral concomitant antibiotic for HS is medically necessary, the UCB Study Physician must be contacted for approval. If systemic antibiotics are used concomitantly, the dose should remain stable and constant.

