6.6.2 Concomitant medication definition

A medication with a start date that is on or after the date of first dose of IMP will be classified as a 'concomitant medication'.

Any medication that started prior to the first dose of IMP and continued after will be classified as both prior and concomitant. Such medications will therefore be counted in the tabulations for both prior and concomitant medication.

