8.2.3.5 Concomitant antibiotic use – Bayesian analysis

The primary Bayesian analysis of HiSCR at Week 12 will be repeated including treatment group, Baseline Hurley Stage, concomitant antibiotic use at study entry (coded as a binary [yes/no] variable) as an additional covariate, and a concomitant antibiotic use × Baseline Hurley Stage interaction term.

The results of this analysis will be presented as specified in [Section 8.2.2.4](#).

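### The SAP's flag for antibiotic use at study entry also counts antibiotics that ended during Screening, two to four weeks before the first dose

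*SAP*

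**What the plan says.** SAP 6.6 sets the flag by two dates only: "any antibiotic with start date on or prior to first dosing, and end date on or after screening". The drug need not still be in use at Baseline.

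SAP 6.6.1 calls a drug prior if it started before the first dose. SAP 6.6.2 treats such a drug as concomitant too only if it carried on: "Any medication that started prior to the first dose of IMP and continued after will be classified as both prior and concomitant".

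The protocol dates that matter are these:

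- **Screening (5.1.1):** "up to a maximum of 4 weeks prior to randomization (dosing cannot occur earlier than 2 weeks after Screening", so 14 to 28 days.
- **Exclusion 7:** "Subject received prescription topical therapies for the treatment of HS within 14 days prior to the Baseline Visit". Protocol 2.1.2 names topical antibiotics among HS treatments.
- **Exclusion 8:** "Subject received systemic non-biologic therapies for HS with potential therapeutic impact for HS less than 28 days prior to Baseline Visit".
- **Exclusion 12:** the subject "has had an infection requiring systemic antibiotics within 2 weeks of the Baseline Visit".
- **Permitted background oral antibiotic (7.8.1):** allowed if the regimen "has been stable for at least 4 consecutive weeks (28 days) prior to Baseline. The dosing regimen must remain stable throughout study participation".

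SAP 8.2.3.5 enters "concomitant antibiotic use at study entry (coded as a binary [yes/no] variable) as an additional covariate", together with its interaction with Baseline Hurley Stage. SAP 8.2.3.9 does the same in the GEE model. SAP 8.2.5 uses the flag for HiSCR tables and for Week 12 bar charts. SAP 6.6 also gives these antibiotics their own summary.

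**The concern.** The antibiotic analyses look at whether background antibiotic therapy matters for HiSCR. SAP 2.4 gives the planning response rates for a setting in which antibiotics at entry are allowed, and SAP 8.2.2.2 says the strength of any antibiotic-by-Hurley interaction in the historical data is unknown. A flag that pools continuing users with subjects who had stopped answers that question less cleanly.

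The miscoding needs no protocol deviation. A site that stops a topical antibiotic at Screening so that the subject meets exclusion 7 creates it. What is at stake is the quality of the adjustment in two supportive analyses and the meaning of the user subgroup in the descriptive displays.

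**Working it through.** The plan gives no figure for this point, so there is none to reproduce. The check is a count of dates.

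**Inputs.** Let *s* be the days from Screening to first dose, 14 to 28 (Protocol 5.1.1). Let *e* be the days from the antibiotic's end date to first dose. Let *w* be the required drug-free interval: 14 days under exclusion 7, 28 days under exclusion 8. For exclusion 12, I assume that the 2 weeks run back from Baseline to the end of the antibiotic course, so *w* = 14. Baseline is taken as the day of first dose.

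**Conditions.** The subject is eligible if *e* ≥ *w* (inclusive reading) or *e* > *w* (strict reading). The SAP codes yes if *e* ≤ *s*. The start-date condition is always met, because these drugs all began before the first dose.

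**Formula.** For *s* ≥ *w*, the eligible end dates coded yes number *s* − *w* + 1 (inclusive) or *s* − *w* (strict). For *s* < *w* there are none.

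| Screening length *s* | *w* = 14, inclusive | *w* = 14, strict | *w* = 28, inclusive | *w* = 28, strict |
|---|---|---|---|---|
| 14 days | 14 − 14 + 1 = 1 | 0 | 0 | 0 |
| 21 days | 21 − 14 + 1 = 8 | 7 | 0 | 0 |
| 27 days | 27 − 14 + 1 = 14 | 13 | 0 | 0 |
| 28 days | 28 − 14 + 1 = 15 | 14 | 28 − 28 + 1 = 1 | 0 |

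The problem therefore lies with topicals and short infection courses. A systemic HS antibiotic stopped for the 28-day interval is caught on one day at most: last taken on the Screening day, with a full 28-day Screening Period.

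**Side by side with 6.6.1 and 6.6.2.** Take Screening 21 days before dosing and a topical antibiotic last used 18 days before dosing. Under 6.6.1 it is prior. Under 6.6.2 it is not concomitant, because it did not continue after the first dose. Under 6.6 it is concomitant at study entry.

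**After the fix.** Requiring the end date to be on or after the first dose means *e* ≤ 0. No date satisfies both *e* ≤ 0 and *e* ≥ 14, so the count is 0 for both intervals at every Screening length.

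**The case against.** **Study entry may mean Screening.** SAP 6.6 defines its own named concept, while 6.6.1 and 6.6.2 classify drugs against the first dose, so calling this a flat contradiction goes too far. Protocol 11.3.1.1 places the IGRA at study entry and Table 5-1 schedules it at Screening; Protocol 16.1 counts a subject as enrolled on signing consent. The protocol is not uniform, though: exclusion 5 ties study entry to the 14 days before Baseline. Nor does the rule fit the Screening reading. With Screening 28 days before dosing, a course running from day 27 to day 18 before dosing is coded yes, although the subject took it on neither the Screening day nor the dosing day.

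**Medical review will catch it.** SAP 6.6 identifies these antibiotics by dictionary code, recorded indication and medical review, confirmed at the data evaluation meetings before unblinding. It would therefore be wrong to say that indication plays no part. But nothing there lets the review set aside the date rule.

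**Few subjects may be affected.** Protocol 2.1.2 says topical antimicrobials are generally given for mild disease, and this trial enrolls moderate to severe disease. This stands: the number could be small.

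**The models do not report an antibiotic effect.** This also stands. SAP 8.2.3.5 reports arm response rates, their difference and the posterior probability; SAP 8.2.3.9 reports responder percentages and treatment odds ratios. Neither model has a treatment-by-antibiotic term. The flag depends on start and end dates relative to Screening and first dose, in randomized arms, so miscoding is not expected to differ by arm and would mainly weaken the adjustment.

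**Stronger readings.** A reader might also infer that a course first started on the dosing day is wrongly called concomitant. SAP 6.6.2 makes it concomitant, so that is not an inconsistency.

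**Conclusion.** Wrong as written, but minor and confined to supportive analyses. The date rule codes as users some eligible subjects whose antibiotic ended 14 to 28 days before the first dose. That follows from the documents' own dates and rests only on the readings of the 14-day limits stated above. How many subjects this touches is unknown.

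Two larger conclusions are not supported. One is that the trial's result is at risk: the primary model in SAP 8.2.2.1 contains treatment and Baseline Hurley Stage only, and the success criterion rests on that model. The other is a definite loss of contrast. As an illustration only, assume 12 of 80 subjects continue an antibiotic and 4, 8 or 12 others are miscoded. Then 4/16 = 25%, 8/20 = 40% or 12/24 = 50% of the user group is off drug. If those subjects respond like non-users, the user versus non-user difference in response rate shrinks to 75%, 60% or 50% of its size (ignoring any change in the non-user group). None of these counts comes from the documents, and that contrast appears only in the descriptive outputs of 8.2.5.

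**What to change.** In SAP 6.6, replace the date rule with: *start date before first dose and ongoing at first dose (end date on or after first dose, or no end date)*. Use this flag in 8.2.3.5, 8.2.3.9 and 8.2.5 and in the separate summary in 6.6. List antibiotics that ended during Screening as prior medication.

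A restriction to systemic HS antibiotics could be added as a further display, but it should not replace this rule. A definition that demanded an HS indication and 28 days of stable use would code as a non-user a subject taking an antibiotic at first dose who began it 20 days earlier or for another reason.

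The cost is one sentence and one changed derivation. It uses medication start and end dates, which the present rule already needs. A course first started on the dosing day would leave the flag but stay in the concomitant medication tables under 6.6.2.
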